Dose Finding. Escalating dosages of intranasal ketamine will be given during the study in order to find optimal analgesic dose without significant side effects. On the first study visit, after obtaining written informed consent, 10mg of intranasal ketamine will be given to make sure that the study patients are able to tolerate a small dose of NAS ketamine. On the second visit, 10 mg of IV ketamine will be given to help establish bioavailability of NAS ketamine, with patients serving as their own controls. On the third and fourth visit, higher doses of ketamine, 30 mg and 50 mg respectively, will be given, if the patients did not have severe adverse events with the smaller dosage. Licensed study personnel delegated to do so, will administer ketamine. The intranasal ketamine will be administered as follows: 1) Ensure mucosal atomization device (MAD) is primed and the appropriate dose loaded into the syringe. 2) Have patient sit in chair and clear sinuses using a tissue if needed. 3) Tilt the patient's head back. 4) Insert MAD into nostril and aim directly posterior, level with the floor of the nare, and slightly lateral. 5) Administer 0.1mL (10mg). 6) Have patient keep his head tilted back for 5 minutes, if tolerable, to ensure that the medication does not run out of nares. Make a note if medication is visibly noted to run out of nares or if patient reports feeling of medication trickling down his throat. 7) If more than 0.1mL (10mg) needs to be delivered, repeat steps 3-5 in the contralateral nare, alternating until the full dose is delivered. Ensure 30 seconds have passed before re-administration into the same nare. Patients may continue to take their usual pain medication as needed. Since most of the oral immediate release opioid medications peak between 30 to 90 minutes, ketamine will be given at least 120 minutes after the last dose of immediate release opioid medication so the reduction in pain score is not confounded with the results of immediate release opioid medications. Pain scores will be recorded on NPRS prior to and at 5, 10, 15, 30, 45, 60, 120, and 180 and 240 minutes after administration of test medication. NPRS is the most responsive tool to document pain intensity when compared to Visual Analogue Scale (VAS) and Visual Rating Scale (VRS) for measuring pain,²⁹ showing higher compliance rates, better responsiveness, ease of use, and good applicability relative to VAS/VRS³⁰. In general, improvements of pain severity</=1.5 points on NPRS could be seen as clinically irrelevant³¹⁻³⁴. Above that value, the cutoff point for "clinical relevance" depends on patients' baseline pain severity, and ranges from 2.4 to 5.3³³⁻³⁵. Higher baseline scores require larger raw changes to represent clinically important differences³⁶.

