At home, patients will log pain scores 3 times a day. 10 item PROMIS questionnaire will be filled out at first (baseline) and fifth (final) study visit to assess global health. Participants will fill out a PHQ-9 scale during the screening visit or the first study visit. PHQ-9 scale ranges from 0 to 27 and can be used for screening of depression. Patients who are on antidepressants or score more than 4 on PHQ-9 scale will be assessed for depression during the study. Depression will be assessed on the MADRS on each visit. (*See appendix 1 F*) This is a 10 item questionnaire designed to be particularly sensitive to treatment effects³⁷. Higher MADRS score indicates more severe depression, and each item yields a score of 0 to 6. The overall score ranges from 0 to 60. Participants who screen positive for depression and are not on any treatment for depression, will be offered a psychiatry consult as a part of their routine healthcare, if interested. Performance status will be assessed on ECOG grading at baseline and throughout the study, which ranges from 0 to 5, where 0 is fully active and 5 is dead. ESAS will be used to assess 9 common symptoms (pain, tiredness,

nausea, depression, anxiety, drowsiness, appetite, well-being, and shortness of breath) experienced by cancer patients. Each symptom is rated from 0 to 10 on a numerical scale; with 0 meaning that the symptom is absent and 10 that it is the worst possible severity. Patient's study participation will end with the 5th and final study visit. Patients will be followed up in the pain or supportive oncology clinic for their routine care for pain management. They will be followed up more frequently if needed. Patients who benefit from intranasal ketamine would be offered this medication as an outpatient. The dosage and regimen will be decided on a case by case basis by the treating physician.

C.3 Monitoring and Documentation: (See appendix 1 for all scales)

The following assessments will be documented in patient research study record:

1. Height and weight at the first study visit
2. Pain intensity on NPRS prior to and at 5, 10, 15, 30, 45, 60, 120, 180 and 240 minutes after medication is given
3. Vital signs including heart rate, blood pressure, respiratory rate and pulse oximetry at baseline, and 5, 10, 15, 30, 45, 60, 120, 180 and 240 minutes. Vital signs and pulse oximetry will be monitored continuously for a minimum of 30 minutes post drug administration. More frequent vital signs if they are unstable

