4. ECOG and ESAS score at baseline on each visit
5. Sedation level on RASS scale prior to and at 30, 60 and 240 minutes after medication is given
6. If RASS score is between +4 to -3 then sedation/delirium assessment on CAM scale will be done prior to and at 30, 60 and 240 minutes after medication is given
7. Side effects on SERSDA scale prior to and at 30, 60 and 240 minutes after medication is given
8. An olfactory assessment will be performed pre and post study drug administration to determine if the study medication has impacted the sense of smell.
9. Rescue medication taken; if taken, was it taken at the usual interval or longer
10. Patient response to intervention if anything besides change in NPRS is reported
11. Patient and family education regarding maintaining pain diary and reviewing discharge instructions, including when to call study coordinator or report to emergency department
12. PROMIS functional scale on the first and last day of the study
13. Any change in health status during the duration of study
14. Opioid medication pill count at the beginning of each visit
15. Only for visits 1, 3, and 4: If the patient reports symptoms of a significant upper respiratory tract infection (e.g. rhinorrhea, congestion), the study visit will be canceled and re-scheduled at a later date.

16. If changes in sense of smell are noted, a study investigator will be notified, and additional olfactory assessments will be performed, with the frequency and amount of assessments at the discretion of the investigator.
17. The frequency of the assessments may be increased at the discretion of the investigator.

The study nurse will notify the attending physician if any of the following occur:

1. Baseline HR >100 or BP>160/100 or pain score </=3 on NPRS who will make the decision of whether or not to proceed with the study visit or cancel based on the inclusion/exclusion criterion
2. After the study medication is given, vital signs change more than 20% from baseline; HR<50 or >110, SBP<90 or >180, DBP<30 or >100, RR<8 or >24 or SaO₂<90; Any side effects or unexpected results
3. Sedation on RASS scale between -1 and -5 at any time
4. Positive for delirium on CAM scale at any time
5. Presence of any possible side effects from the study drug administration

Patients will be deemed eligible for discharge after the 240 minute assessment if they meet the following:

- Vital signs are within 10% of baseline values
- RASS score is between +1 and -1

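### Respiratory rate and oxygen saturation are measured before every dose, but neither can trigger the pre-dose physician call

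*Combined protocol and SAP*

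**What the plan says.** Assessment 3 in C.3 requires "Vital signs including heart rate, blood pressure, respiratory rate and pulse oximetry at baseline" and at set times up to 240 minutes. Footnote 7 of the Table of Assessments applies this to Visits 1 to 4, the four dosing visits.

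C.3 then lists when the study nurse must notify the attending physician:

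- Item 1, before dosing: "Baseline HR >100 or BP>160/100 or pain score </=3 on NPRS". The physician then decides whether to proceed or "cancel based on the inclusion/exclusion criterion".
- Item 2 opens with "After the study medication is given, vital signs change more than 20% from baseline" and goes on to absolute limits, among them RR <8 or >24 and SaO2 <90. It also covers side effects and unexpected results.
- Item 3: "Sedation on RASS scale between -1 and -5 at any time". Item 4 does the same for a positive CAM result. Both therefore cover the baseline assessment.
- Item 5: possible side effects of the study drug.

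The C.9 exclusions cap blood pressure (item 5) and heart rate (item 6). The nearest respiratory exclusion (item 2) concerns a disposition to laryngospasm or apnea and gives no value. Under Respiratory effects, C.5 describes respiratory depression as RR <10/min and saturation <90%, separated by a comma. It requires the study physician to be told if this persists at the end of the visit.

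**The concern.** The plan collects two respiratory measurements just before giving the drug and attaches no action to them at the one moment when the dose could still be withheld. Once the drug is in, the plan treats the same values as reason for a call.

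The population makes this relevant. C.2 (Concomitant Opioid medications) expects subjects to be taking opioids. One route to eligibility under C.8 is an oral morphine equivalent of at least 50 mg/day. C.5 names opioid co-administration as a setting in which ketamine can depress respiration. Delegated licensed personnel give the dose (C.2, Dose Finding), and no physician review of baseline vital signs is described. What is at stake is patient safety at the point of dosing, not the endpoints or the analysis.

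**Working it through.** The plan gives no figure of its own here, so the check is mainly a comparison of rules.

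**Step 1. Does any rule require a call before dosing?** Take a patient who is RASS 0, CAM-negative, with HR ≤100, BP ≤160/100 and NPRS ≥4, and with SaO2 88% or RR 7 (illustrative values).

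| Rule | RR or saturation value | In force before the dose? | Call required before the dose? |
|---|---|---|---|
| C.3 notification item 1 | none | yes | no |
| C.3 notification item 2 | RR <8 or >24; SaO2 <90; change >20% | no | no (yes at first post-dose reading) |
| C.3 item 3 (RASS) | none | yes | no, RASS is 0 |
| C.3 item 4 (CAM) | none | yes | no, CAM is negative |
| C.3 item 5 | none | concerns drug effects; cannot apply before the first dose | no |
| C.8 and C.9 eligibility | none | yes | no |
| C.5 respiratory rule | RR <10, saturation <90% | no, end of visit | no |

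No rule requires a call. Reading item 2's limits as pre-dose limits would contradict its opening words and make part of item 1 redundant.

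**Step 2. What happens after the dose?**

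- *Saturation.* An SaO2 below 90 at any post-dose reading meets item 2, so a physician is called. A baseline of 88% gives a discharge band ("Vital signs are within 10% of baseline values") of 88 × 0.9 = 79.2% to 88 × 1.1 = 96.8%. Any post-dose value in the part below 90% has already required a call.
- *Respiratory rate.* C.5 counts RR 8 or 9 as depression (<10), but item 2's absolute limit is <8. The relative rule (a change of more than 20%) reaches RR 9 only if baseline exceeded 9 / 0.8 = 11.25, and RR 8 only if baseline exceeded 8 / 0.8 = 10. From a baseline of 9, a fall to 8 is 1/9 = 11%, so it is not flagged. An RR unchanged at 9 also meets the 10% discharge rule. Among the numeric rules, only the C.5 end-of-visit check then remains, and its comma leaves open whether one value is enough.

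**Step 3. How many checks are involved?** There are four pre-dose checks per fully treated patient.

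- Minimum of 10 completers: 10 × 4 = 40 checks.
- All 25 planned enrollees receiving every dose: 25 × 4 = 100 checks.

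The documents give no frequency of low baseline RR or saturation in alert patients. Assuming 1% to 5% of checks would meet a new trigger:

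- 40 checks: 40 × 0.01 = 0.4 to 40 × 0.05 = 2 calls.
- 100 checks: 100 × 0.01 = 1 to 100 × 0.05 = 5 calls.

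**The case against.** The best defence is that item 1 is an eligibility re-check. Its values match exclusions 5 and 6 and the NPRS threshold in the inclusion criteria, and its focus on high heart rate and pressure fits the cardiovascular effects described in C.5. The affected patient must also meet several conditions at once: alert, CAM-negative, in pain of at least 4, within the heart-rate and pressure limits, and yet with a low RR or saturation. C.5 calls respiratory depression rare. The analgesic regimen must have been stable for more than 7 days. Ketamine is given at least 120 minutes after the last immediate-release opioid, beyond the 30 to 90 minute peak that C.2 cites. Pulse oximetry runs continuously for at least 30 minutes after dosing.

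All of this stands as mitigation and keeps the point modest. None of it supplies a pre-dose call. The 120-minute interval is justified by confounding of pain scores and does not cover long-acting opioids. Clinical judgement may fill the gap, but the plan does not require it to.

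A second objection is that RR <10 before the dose sits oddly with RR <8 after it. This does not hold, because item 1 is already stricter than item 2 on heart rate (100 against 110) and systolic pressure (160 against 180).

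**Conclusion.** The gap is real and narrow. An alert, CAM-negative patient inside item 1's limits can be dosed with a low RR or saturation and no required call, although SaO2 <90 or RR <8 would require one at the first post-dose reading. The number affected is unknown and probably small; the 0.4 to 5 calls rest wholly on the assumed 1% to 5%. The remaining post-dose weak spot is RR 8 to 9. This is an inexpensive safety improvement that should be made, not a defect in the endpoints.

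A reader might infer three stronger things that the documents do not support:

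- *That C.5 is the only absolute limit on saturation.* Item 2 also sets SaO2 <90 throughout the post-dose readings, so the wide discharge band does not let a desaturated patient leave without a physician having been called.
- *That respiratory values alone are left open at baseline.* Heart rate and pressure are limited only on the high side. A baseline HR below 50 or SBP below 90, both listed in item 2, triggers nothing in item 1 either.
- *That the IV visit lacks a respiratory safeguard the other visits have.* The rule that begins "Only for visits 1, 3, and 4: If the patient reports symptoms of a significant upper respiratory tract infection" covers exactly the intranasal visits ("On the second visit, 10 mg of IV ketamine will be given") and gives rhinorrhea and congestion as examples. It reads as a nasal-delivery rule, so its absence at Visit 2 is expected.

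**What to change.** In C.3 notification item 1, add: *RR <10 or SaO2 <90 (either one)*, for all four dosing visits. These are the C.5 values; the words in brackets avoid the ambiguity of the C.5 comma. State as well that the physician may postpone or cancel the dose on respiratory grounds. Without that sentence the call would lead to a decision tied to eligibility criteria that contain no respiratory values.

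The cost is one line plus that sentence. Both measurements are already taken, and endpoints, analysis and sample size do not change. The downside is a few extra physician calls and an occasional postponed visit.

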- Side effects as noted on the SERSDA scale are valued as 2 or less, or no more than 1 point greater than their baseline value. Investigator must be notified if value is greater than 2.

Should the patient not meet these criteria at the end of the 240 minute assessments, the study nurse will contact the research physician for further evaluation and assessment.

C.4 Potential Risks

Adverse effects are dose related. No serious side effects have been reported with intranasal ketamine doses of up to 50 mg.

Common side effects of ketamine: Include sedation, somnolence, sensory illusions, dissociative feelings, blurred vision, anorexia, abdominal pain ^{38, 39}, feeling of insobriety ^{40, 41}, and dream disturbances ⁴². Dose-dependent side effects include hallucinations, agitation, nightmares, dizziness, and nausea ⁴³. At higher doses, side effects may include delirium, impaired motor function, amnesia, anxiety, panic attacks, mania, insomnia, and elevated blood pressure ⁴³. Rarely, hepatic failure⁴³ has been reported in participants with

underlying liver disease prior to ketamine administration. Additionally, chronic administration of ketamine has been associated with ulcerative or hemorrhagic cystitis, which usually resolves with cessation of ketamine administration⁴³. However this was reported in ketamine abusers and dosage being used for this study are very low. Additionally, a LFT and UA will be done the day of or up to 24 hours before both visits 1 and 5 to monitor for rare side effects. If obtained as standard of care within this time frame, these will not need to be repeated for the study. Benzodiazepines and neuroleptics have been used to successfully minimize psychotomimetic effects, such as psychosis or delirium, when ketamine is used for the treatment of pain^{44, 45}.

C.5 Management of specific side effects

Side effects unique to intranasal route: Include transient change in taste, rhinorrhea and nasal passage irritation. If the patient reports that these changes to be persistent beyond the date of administration of study drug and are moderate to severe in intensity, then a formal ENT consult will be sought.

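### The C.3 discharge list is looser than the protocol's own safety thresholds on oxygen saturation and on oral-liquid tolerance

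*Combined protocol and SAP*

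**What the plan says.** C.3 (Monitoring and Documentation) sets three conditions for discharge after the 240-minute assessment:

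- Vital signs: "Vital signs are within 10% of baseline values". Item 3 of the same section defines what is measured: "Vital signs including heart rate, blood pressure, respiratory rate and pulse oximetry at baseline". Saturation is therefore inside the band.
- Sedation: "RASS score is between +1 and -1".
- Side effects: SERSDA scores "valued as 2 or less, or no more than 1 point greater than their baseline value", with the rider "Investigator must be notified if value is greater than 2".

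If the list is not met, the consequence is: "Should the patient not meet these criteria at the end of the 240 minute assessments, the study nurse will contact the research physician". That doctor then evaluates the patient.

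A separate C.3 list tells the nurse when to notify the attending physician. After dosing this includes "RR<8 or >24 or SaO₂<90; Any side effects or unexpected results", and also "Sedation on RASS scale between -1 and -5 at any time".

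C.5 (Management of specific side effects) has end-of-visit rules of its own. Under respiratory effects it puts a rate below 10/min and a saturation below 90% in one bracket, separated by a comma. If these persist at the end of the visit, the study MD is notified; the sentence first says that admission will be considered and then that the patient will be admitted. Under gastrointestinal effects it orders admission, without qualification, when oral liquid is not tolerated. Under ocular effects it has the study MD choose between discharge and 23-hour observation.

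**The concern.** A discharge checklist should not pass a patient whom another part of the same protocol treats as unfit to leave. Here it can do so in two ways. A relative band lets saturation fall below 90% whenever the baseline is moderately below 100%. And the one gastrointestinal state for which C.5 orders admission is not on the list: SERSDA scores nausea but neither vomiting nor fluid intake.

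What is at stake is patient safety at the moment of going home; no endpoint, analysis or sample size is affected. C.5 itself notes that respiratory depression can occur when ketamine is combined with opioids. Patients here may continue their usual pain medication, and entry requires either frequent breakthrough dosing or at least 50 mg/day of oral morphine equivalent.

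**Working it through.** **Inputs.** 10% discharge band, 20% change trigger and saturation trigger of 90 (C.3); saturation limit of 90% and rate limit of 10/min (C.5); heart-rate and blood-pressure entry limits (C.9); SERSDA range 0 to 4 (Appendix I-B). The documents give no baseline saturations, so whole-number baselines of 90 to 100% are enumerated.

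**Saturation.** Lowest passing value = 0.9 × baseline.

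| Baseline (%) | 0.9 × baseline | Readings below 90 that pass |
|---|---|---|
| 90 | 81.0 | 81–89 |
| 92 | 82.8 | 83–89 |
| 94 | 84.6 | 85–89 |
| 95 | 85.5 | 86–89 |
| 96 | 86.4 | 87–89 |
| 97 | 87.3 | 88–89 |
| 98 | 88.2 | 89 |
| 99 | 89.1 | none |
| 100 | 90.0 | none |

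Odd baselines 91 and 93 give 81.9 and 83.7, so 82–89 and 84–89 pass. Reading the band strictly rather than inclusively changes only one entry: 81 no longer passes from 90. Reading it as 10 percentage points would let 89 pass from a baseline of 99 as well.

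**Does the 20% change trigger catch these readings?** No. 0.8 × 90 = 72, 0.8 × 95 = 76 and 0.8 × 98 = 78.4, all below the readings in the table. Among the numeric triggers, only the absolute one at 90 does.

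**Respiratory rate.** From a baseline of 10 the band is 9.0 to 11.0, so 9 passes. From 11 it is 9.9 to 12.1, so nothing below 10 passes. The rate gap therefore exists only at baselines of 10 or lower. It follows that, if the C.5 bracket needs both signs together, a patient can pass the band and meet C.5 only at those baselines. The mismatch with the C.3 saturation trigger does not depend on how the comma is read.

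**Heart rate and blood pressure.** From the highest eligible baselines: 1.1 × 100 = 110 (C.5 limit above 120), 1.1 × 160 = 176 (above 180), and diastolic 1.1 × 100 = 110 (above 110). There is no conflict with the absolute C.5 limits.

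**Oral liquid.** Set against the C.5 admission rule, none of the three items asks about intake. The nearest is SERSDA nausea, and a score of 4 from a baseline of 3 passes, being one point higher.

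**Does notification by itself hold discharge?** The list shows that it need not. Read inclusively, RASS -1 triggers notification and also meets the sedation item. A SERSDA score of 3 from a baseline of 2 passes, with the investigator told. A diastolic pressure of 105 from a baseline of 100 is within the band (up to 110) and above the notification limit of 100.

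**The case against.** The strongest reply is that every patient in question already reaches a physician. Saturation below 90 and any side effect are notification triggers in C.3, and C.5 adds its own notification for respiratory depression. Failing the discharge list would itself lead only to a call to the research physician, so adding items seems to change little. C.5 can also be read as cumulative: an order to admit overrides a statement of eligibility, and the ocular rule shows C.5 deciding discharge on a sign outside the vital-sign and RASS items. C.5 calls respiratory depression rare, patients are watched for 240 minutes after a supervised dose, and exclusions 2 and 21 in C.9 (laryngospasm or apnea, intractable vomiting) narrow the risk at entry. The study-specific operating procedure mentioned in C.13 item 2e may hold a fuller checklist; it is not in the documents.

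Most of this stands, and it limits the consequence. A reader might infer that the plan sends hypoxic or vomiting patients home with no physician involved, or that C.5 has no bearing on discharge. The documents support neither: notification is required, and the ocular rule links C.5 to discharge directly. Nor does tolerance of drowsiness or a near-baseline SERSDA score prove that a saturation below 90% may be ignored.

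What does not fall away is the classification. The list calls such a patient eligible. The ocular sentence covers ocular effects only, and no general sentence says that discharge waits for the physician who has been notified.

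**Conclusion.** The point holds as a mismatch between sections, not as a missing safeguard. For whole-number baselines of 90 to 98%, the discharge band accepts between one and nine readings below 90%; at 99 and 100% it accepts none. The widest ranges need a baseline near 90%, and because baseline saturations are not given, how often this would arise is unknown. The result rests on pulse oximetry being a vital sign, as C.3 item 3 says, and on a relative reading of 10%.

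The conflict with the C.3 notification threshold is certain. A conflict with C.5 on saturation is general only if either respiratory sign is enough, which the wording leaves open; to call it a flat contradiction would go further than the text. The oral-liquid gap needs no such assumption: C.5 orders admission, and the list does not ask. The amendment should be made because it is cheap and concerns safety, but the existing notification rules keep it from being critical.

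**What to change.** In C.3, state that a patient who meets any C.5 admission or respiratory-depression criterion at the 240-minute assessment is not eligible for discharge until the study physician has evaluated them. For saturation, replace the 10% band with a requirement of at least 90%. Since 0.9 × 100 = 90, this does not loosen the lower limit for any baseline up to 100%. Add tolerance of oral liquid to the list. In C.5, state that either a rate below 10/min or a saturation below 90% is enough.

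Two additions are optional. One is a rate floor of 10/min, added to the 10% band so that the upper limit stays. The other is a hold on discharge after a positive 240-minute CAM until a physician has evaluated the patient; this would tighten C.3's own notification rule and does not resolve any conflict with C.5.

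The cost is a wording amendment, a revised checklist and a brief oral-liquid check; saturation and rate are already recorded at 240 minutes. There will be occasional extra physician evaluations, including for a patient whose usual saturation is below 90%. If the rate floor is adopted, the same applies to a patient whose usual rate is 9 or lower: from 9 the band ends at 9.9, so band and floor cannot both be met.
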